3. STUDY DESIGN

This is a single center, mechanistic study in which 88 healthy subjects will be stratified by age with 22 subjects (ages 25-40) and 66 subjects (ages 60-89). and randomized to receive PPV23 or PCV13 in a 1:1 ratio.

Study volunteers will be recruited from the general population of metropolitan Atlanta. The study will be conducted at the Hope Clinic of the Emory Vaccine Center (Decatur, GA). The expected duration of subject participation is 6 months. An additional optional blood draw will be offered 2-3.5 years after enrollment.

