7. STUDY VISITS AND PROCEDURES

7.1 Enrollment and Randomization

This research study will be explained in lay terms to each potential research participant. The potential participant will sign an informed consent form before undergoing any study procedures. Participants who are deemed eligible for the study (see sections 4.1 and 4.2) will be enrolled and assigned a unique participant number. Approximately eighteen months are needed for enrollment. The duration of participation for each subject is approximately 6 months. An additional optional blood draw will be offered 2-3.5 years after enrollment.

Eighty eight subjects (22 subjects (ages 25-40) and 66 subjects (ages 60-89)) will be randomized to receive PPV23 or PCV13 in a 1:1 ratio.

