7.4 Main Study Visit(s)

All participants will return for the study-related blood draws on Days 1, 3, $7(\pm 1)$, $14(\pm 2)$, $30(\pm 7)$ 180 (± 14) and year 2-3.5 (optional visit) after immunization. These visits will last approximately 20 minutes.

On days 1, 3, 7, 14, 30 and 180 study personnel will review current health status including:

- Evaluation of local REs and systemic REs of grade 3 or higher severity developing after the last visit (only until Day 7 Visit).
- Any adverse event (AE) that limited self-care activities of daily living or serious adverse event (SAE) which may not have been reported by the participant by calling the site as directed at a prior visit.
- Any medications administered after vaccination.

At the end of the visits on days 1, 3 and 7, 14 and 30 the participant will be instructed to promptly call the site if he/she becomes sick or has been treated at the doctor's office or emergency department or has been hospitalized for any illness throughout D180 of the study. The participant will also be instructed to call the site if he/she develops any adverse event that limits self-care activities of daily living even if he/she decides not to get medical care, or starts/stops any medications/therapies.

Refer to section 8.2.5 for safety data that must be recorded and reported.

A focused physical exam will be conducted -if indicated- based on results of the review of health status as above.

At year 2-3.5 visit, participant will be asked about any major change in health status and if they have received any pneumococcal vaccine since last study visit.

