Both for sample size consideration and data analysis, we will use different stringency levels for the traditional immune parameters and microarray data, because the traditional immune parameters are measured with less noise, and a traditional immune parameter is more likely than an average gene to be associated with the immune response.

Primary Endpoint 1.

The innate signatures will be detected in each treatment group separately. A two-sided paired paired t-test will be used to test each immune parameter, in order to find immune parameters that change significantly over the baseline. As multiple immune parameters are studied, we use the alpha level of 0.01 to offset multiple testing. With 30 samples in each treatment group in the elderly, we can reject the null hypothesis of equal means with 80% power if the true effect size (mean difference/sigma) is 0.66, using a two-sided paired t-test and the alpha level of 0.01.

For the gene expression, again the innate signatures will be detected in each treatment group separately. The actual data analysis will be performed using the method Significance Analysis of Microarrays (SAM) with paired design. For sample size consideration, we will consider the simpler case of a paired t-test. As the number of genes tested is in the order of tens of thousands, we use the alpha level of 0.0005 to offset the effect of multiple testing. This means an average of one false positive for every 2000 null genes tested, which is an acceptable level as we expect >100 truly differentially expressed genes. In actual data analysis false discovery rate (FDR) will be used. With 30 samples in each elderly treatment group, we can reject the null hypothesis of equal means with 80% power if the true effect size (mean difference/sigma) is 0.88, using a two-sided paired t-test and the alpha level of 0.0005.

Primary Endpoint 3, Secondary Endpoints 2&4.

The correlation signatures will be identified for each treatment group separately. The innate signature markers/genes identified in the analysis of Primary Endpoint 1 will be used in this step for the identification of correlation signature. For the traditional immune parameters, with 30 samples in each elderly treatment group, at the alpha level of 0.01, we can reject the null hypothesis of zero correlation with 80% power if the true correlation is 0.57 using a two-sided test for Pearson's correlation coefficient.

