The innate signatures will be detected in each elderly treatment group separately. We will take the measurements on the day of vaccination as baseline. For traditional immune parameters, we will test if an immune parameter shows significant change over baseline at day 1, 3, and 7 after each vaccination, using a two-sided paired t-test. In addition, for each immune parameter, the fold-change over baseline will be calculated for every subject. The average (arithmetic mean) fold change over the 30 subjects will be combined with the test p-value in a selection criterion as appropriate. Based on previous studies similar in nature, the tentative selection criterion is pvalue ≤ 0.01 and average fold change ≥ 3 .

For the gene expression data, again the innate signatures will be detected in each elderly treatment group separately. We will use the method Significance Analysis of Microarrays (SAM) ³⁴ with paired design to find differentially expressed genes over the baseline. False discovery rate (FDR) will be used as selection criterion. The tentative selection criterion is FDR \leq 0.1.

2. Measurement of adaptive immune responses [Opsonophagocytosis assay (OPA) titers] at day 30 post vaccination with either PPV23 or PCV13 in the elderly.

The OPA titers will be presented as descriptions of the actual values separately in both study elderly populations (PPV23 and PCV13 recipients). Summary statistics, boxplots and histograms will be used to summarize the data.

3. Correlation of signatures of generic innate immune responses at days 1, 3 and 7 that correlate to adaptive immune responses [Opsonophagocytosis assay OPA titers] at day 30 post vaccination with either PPV23 or PCV13 in the elderly.

The correlation signatures will be detected in each elderly treatment group separately. The innate signature markers/genes identified in Primary Endpoint 1 will be used in this step for the identification of correlation signature.

For traditional immune parameters, we will calculate the correlation coefficient between the immune parameter and the adaptive immune response (day 30 OPA titers). The p-values associated with the correlation coefficients will be used to select traditional immune parameters

that are associated with the respective adaptive immune responses (day 30 OPA titers). The tentative selection criterion is p-value ≤ 0.01 .

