For gene expression data, we will use the method Significance Analysis of Microarrays (SAM) with quantitative outcome to identify genes that are significantly associated with the respective adaptive immune responses (day 30 OPA titers). False discovery rate (FDR) will be used as selection criterion. The tentative selection criterion is FDR ≤ 0.1 .

Analyses of secondary endpoints:

1. Comparison of the serotype specific IgG levels at day 30 post vaccination with either PPV23 or PCV13 in the elderly.

Descriptive analysis, boxpots and histograms, will be conducted to present the data. Testing between the two elderly treatment groups will be conducted using unpaired t-test after proper data transformation. In the case that near-normality cannot be achieved with data transformation, we will resort to the Wilcoxon test.

2. Correlation of signatures of generic innate immune responses at days 1, 3 and 7 with serotype specific IgG levels at day 30 post vaccination with either PPV23 or PCV13 in the elderly.

The analysis will be conducted in each elderly treatment group separately. For traditional immune parameters, we will calculate the correlation coefficient between the immune parameter and the adaptive immune response (IgG levels at day 30 post vaccination). The p-values associated with the correlation coefficients will be used to select traditional immune parameters that are associated with the respective adaptive immune responses (IgG levels at day 30 post vaccination). The tentative selection criterion is p-value ≤ 0.01 .

For gene expression data, we will use the method Significance Analysis of Microarrays (SAM) with quantitative outcome to identify genes that are significantly associated with the respective adaptive immune responses (IgG levels at day 30 post vaccination). False discovery rate (FDR) will be used as selection criterion. The tentative selection criterion is $FDR \le 0.1$.

3. Comparison of the serotype-specific avidity indexes in a subset of up to 6 vaccinees per vaccine group at day 180 post vaccination with either PPV23 or PCV13 in the elderly.

Descriptive analysis, boxpots and histograms, will be conducted to present the data. Testing between the two elderly treatment groups will be conducted using unpaired t-test after proper data transformation. In the case that near-normality cannot be achieved with data transformation, we will resort to the Wilcoxon test.

CONFIDENTIAL

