After identifying the innate immune signatures and correlation immune signatures within each elderly treatment group and each young treatment group, there is an interest in comparing the signatures between PPV23 and PCV13 recipients. Here we consider four groups: elderly PPV23, elderly PCV13, young PPV23 and young PCV13. Each group has two signatures – innate signature and correlation signature. For each group, the correlations signature is a subset of the innate signature. For both the innate and the correlation signature, we will make comparisons between:

A-- the two vaccine groups in the same age category: elderly (60-89) receiving PPV23 v.s. elderly (60-89) receiving PCV13 and young (25-40) receiving PPV23 v.s. young (25-40) receiving PCV13),

B-- all the other possible combinations: elderly (60-89) receiving PPV23 v.s. young (25-40)
receiving PPV23; elderly (60-89) receiving PPV23 v.s. young (25-40) receiving PCV13; elderly (60-89) receiving PCV13 v.s. young (25-40) receiving PPV23; elderly (60-89) receiving PCV13
v.s. young (25-40) receiving PCV13.

This part of the analysis will depend on the results of the aforementioned analysis and hard to specify at this stage.

As a preliminary consideration, the identified innate signature variables and correlation signature variables can be contrasted between groups using descriptive statistics, such tabulation and Venn diagrams.

5. Comparison of generic innate immune responses at days 1, 3 and 7 with adaptive immune responses [Opsonophagocytosis assay OPA titers and ELISA] at years 2-3.5 post vaccination with either PPV23 or PCV13.

For correlation analysis, the analysis is similar to primary endpoint 3. Instead of using all the data, we will analyze data in the elderly.

Enriched biological pathways can be identified using each type of signature in each of the four groups considered above (i.e. elderly (60-89) receiving PPV23, elderly (60-89) receiving PCV13, young (25-40) receiving PPV23 and young (25-40) receiving PCV13), using gene ontology (computer program that generates biological networks from gene lists). Then the enriched pathways can be manually compared between the different treatment groups as per #A and #B above. Biological interpretations of the differences will be made.

9.2.2. Patient populations

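### Exploratory endpoint 5 correlates innate markers with titres drawn anywhere from 2 to 3.5 years after vaccination without adjusting for elapsed time, which adds avoidable noise

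*Combined protocol and SAP*

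**What the plan says.** Section 3 describes the late sample this way: "An additional optional blood draw will be offered 2-3.5 years after enrollment". Section 7.4 lists it as "year 2-3.5 (optional visit) after immunization". Section 7.6 and Appendix 1 give no target date inside that range. The other post-vaccination draws are on fixed days (1 and 3) or have narrow windows: day 7 ±1, day 14 ±2, day 30 ±7 and day 180 ±14.

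Exploratory endpoint 5 in section 9.2.1 sets the innate responses against "adaptive immune responses [Opsonophagocytosis assay OPA titers and ELISA] at years 2-3.5 post vaccination with either PPV23 or PCV13". Its correlation method is one line: "For correlation analysis, the analysis is similar to primary endpoint 3. Instead of using all the data, we will analyze data in the elderly". The method it points to has two parts:

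- For immune parameters: "we will calculate the correlation coefficient between the immune parameter and the adaptive immune response (day 30 OPA titers"), with a tentative cut-off of p ≤ 0.01.
- For genes: "Significance Analysis of Microarrays (SAM) with quantitative outcome to identify genes that are significantly associated with the respective adaptive immune responses (day 30 OPA titers"), with a tentative FDR ≤ 0.1.

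Both are run within each elderly vaccine group, and neither has a covariate. Nothing in the analysis plan adjusts for the time from vaccination to the late draw, restricts it or stratifies by it. Section 7.4 and Appendix 1 have the site record any pneumococcal vaccine received outside the study before the late visit, but no analysis rule uses that record.

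**The concern.** A correlation designed for a draw with a 14-day window (day 30 ±7) is reused for a window of 1.5 years, about 548 days and so about 39 times wider. If antibody is still falling between years 2 and 3.5, two subjects with the same underlying persistence will show different titres because one was bled later. That variation has nothing to do with the innate markers. It dilutes any true correlation, although the interval that causes it can be calculated for every subject.

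This is the only listed endpoint that correlates innate markers with OPA or IgG titres after day 30, and the synopsis objective and section 2.2 both name persistence. The draw is optional, so the sample may fall below the 30 per group assumed for primary endpoint 3, and avoidable noise then costs more.

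**Working it through.** **The plan's own figure.** Section 9.1 states, "With 30 samples in each elderly treatment group" and two-sided alpha 0.01, 80% power for a true correlation of 0.57. Fisher's z with the t-based critical value and bias correction gives 79.2%, so the figure reproduces. The plan gives no figure for exploratory endpoint 5. I use 0.57 at n = 30 as the reference because the method is borrowed.

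**Inputs.** The window is 1.5 years (sections 7.4 and 7.6). Decay rate and titre SD are not in the documents. I assume half-lives h of 1 to 5 years and a between-subject SD s of 0.4 or 0.6 log10.

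**Formulas.**
- Decay slope: b = log10(2)/h per year.
- Fold fall across the window: 10^(1.5b).
- SD of the interval for evenly spread draws: 1.5/√12 = 0.433 years.
- Share of titre variance due to the interval: (0.433b)² / [(0.433b)² + s²].
- Attenuated correlation, if the interval is unrelated to the marker: 0.57 × √(1 − share).

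Worked example, h = 1 and s = 0.4: b = 0.301; 0.433 × 0.301 = 0.130; share = 0.0170/(0.0170 + 0.16) = 9.6%; r = 0.57 × √0.904 = 0.542.

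| Half-life | Fold fall over 1.5 y | Share, s = 0.4 / 0.6 | r, s = 0.4 / 0.6 | Power at n = 30, s = 0.4 / 0.6 |
|---|---|---|---|---|
| 1 y | 2.83 | 9.6% / 4.5% | 0.542 / 0.557 | 72.5% / 76.2% |
| 2 y | 1.68 | 2.6% / 1.2% | 0.563 / 0.567 | 77.5% / 78.4% |
| 3 y | 1.41 | 1.2% / 0.5% | 0.567 / 0.569 | 78.4% / 78.8% |
| 5 y | 1.23 | 0.4% / 0.2% | 0.569 / 0.570 | 78.9% / 79.1% |

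If draws cluster at the two ends of the window, the interval SD is at most 0.75 years. The 1-year half-life then takes 24% (s = 0.4) or 12% (s = 0.6) of the variance.

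**If the interval were also related to a marker.** I simulated n = 30 with evenly spread draws, no true marker-titre link, the same half-lives and SDs, and a test at nominal 0.01 (40,000 runs per case).
- Marker-interval correlation 0.5: the plain test rejects in 1.0% to 3.8% of runs.
- Marker-interval correlation 0.9: 1.1% to 13.8%.
- Partial correlation given the interval: about 1% in every case.
- Residualising the titre but not the marker: about 0.3% at correlation 0.5 and practically never at 0.9. That is too conservative and would also hide real correlates, so both variables must be adjusted.

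**Sample size.** The number attending is not stated. At two-sided alpha 0.01, 80% power needs r = 0.68 at n = 20 and r = 0.75 at n = 15.

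**The case against.** The case against giving this much weight is strong, and most of it stands.

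- The endpoint is exploratory, the draw is optional, the cut-offs are tentative, and section 9.1 calls the study explorative. This limits the stakes.
- Section 9.4 allows alternative approaches ad hoc, so an interval term could be added later. It does not mention the interval, though, and an adjustment chosen after seeing the data is weaker than one written beforehand.
- The documents hint at slow late decay. Section 1.6.1 cites a study in which IgG and functional antibodies in people over 65 stayed above baseline five years after PPV23. A sustained 1-year half-life would be a 2⁵ = 32-fold fall in five years. No rate is given, so this does not settle the matter, but the top of the assumed range is the least supported part of it.

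A reader might go further and infer that elapsed time creates false correlates. Section 7.1 says "Approximately eighteen months are needed for enrollment", which matches the length of the late window, so the interval might seem to be fixed by enrolment date and hence tied to season or assay batch. The documents do not support this. They do not say that late draws are made in one short calendar period, or in what order samples are assayed. Season is a weak route in any case: over 18 months of even enrolment, an annual sine wave correlates with enrolment date at no more than 0.11 in absolute value, whatever its phase.

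A reader might also attribute the whole difference between a 2-year and a 3.5-year titre to waning. That does not follow either, because outside pneumococcal vaccination can intervene and a later draw leaves more time for it.

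**Conclusion.** The omission is real and its effect is small. The stated method treats titres from 2 to 3.5 years as one outcome, which adds noise that could be removed. Under the assumed half-lives, SDs and evenly spread draws, the interval takes about 0.2% to 10% of titre variance, and under 3% for half-lives of 2 years or more. At n = 30 the reference power falls from 79.2% to between 72.5% and 79.1%. These sizes rest on assumed decay and SD, since the documents give neither.

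A spurious or masked correlate is a conditional risk only: it would arise if, for example, late draws were bunched in calendar time and assay batches followed enrolment order. No primary or secondary conclusion is affected. This is a low-priority improvement, worth making because it is cheap.

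**What to change.** In exploratory endpoint 5 (section 9.2.1), within each elderly vaccine group:

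1. For immune parameters, use the partial correlation of each marker with log OPA and with log IgG, given the time from vaccination to the late draw.
2. For genes, residualise both expression and log titre on that interval before SAM.
3. Report the distribution of the interval by arm.
4. Repeat the analysis excluding subjects who report a pneumococcal vaccine outside the study before the late draw. The interval term does not deal with this event, and it is already recorded.

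The cost is one degree of freedom in a small optional sample and a little more analysis work. Visits, samples and data collection stay the same.

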9.2.3 Study Participant Baseline Characteristics and Demographics

Summary of descriptive statistics for baseline and demographic characteristics will be provided for all enrolled participants. Demographic data will include age, race, sex, medical history including medication, vaccination history and previous documented Pneumococcal disease will be recorded.

9.2.4 Status of Study Subjects

Status of study subjects (continue in the study vs. left the study and reasons for discontinuation) will be incorporated to the periodic safety reports.

9.3. Interim Analyses

N/A

9.4. Deviations from Statistical Plan

The principal features of the study design and of the plan for statistical analysis of the data are outlined in this protocol. Any changes in these principal features will require a protocol amendment and will be described in the final report. These changes will be subject to review by the IRB, ISM and NIAID.

Although our statistical methods and time-points for measurements will adhere to what is proposed herein, our experience with analyses of similar studies in the past has underscored the need for flexibility and adaptability in trying different statistical approaches to arrive at the most informative results.

As such, we may use alternative approaches such as the gene set enrichment analyses, or other approaches, and run additional statistical analyses of data generated by use of assays at time points other than those stated in the primary, secondary and exploratory endpoints, on an *ad hoc* basis.

10. IDENTIFICATION AND ACCESS TO SOURCE DATA

10.1 Identifying Source Data

The investigator will keep accurate records to ensure that the conduct of the study is fully documented. Data forms are either considered source or protocol-specific CRFs as detailed in the MOPs.

10.2 Updating Source Documentation

Documents describing the safety profile of investigational products, such as the investigator's brochure and the package insert, will be amended as needed by the investigational products manufacturer to ensure that the description of safety information adequately reflects any new clinical findings.

The Principal Investigator (or co-PI) will provide the ISM, the NIAID Medical Officer, and the IRB with the most up-to-date versions of the above documents as soon as the Principal Investigator (or co-PI) becomes aware of any changes. For purchased investigational products, the Principal Investigator (or co-PI) will confirm that there are no changes to the package insert every 3 months. In case of package insert changes, the Principal Investigator (or co-PI) will notify the ISM, the NIAID Medical Officer, and the IRB.

10.3 Permitting Access to Source Data

The investigator will keep accurate records to ensure that the conduct of the study is fully documented. Data forms are either considered source or protocol-specific CRFs as detailed in the MOPs.

The NIAID will provide the ISM and the Principal Investigator with the most up-to-date version of the package insert of PNEUMOVAX®23 AND PREVNAR®13 as soon as it becomes aware of any changes and the Principal Investigator will, in turn inform the IRB.

HIPC: VAX-003

CONFIDENTIAL

The investigational site participating in this study will maintain the highest degree of confidentiality for the clinical and research information obtained from the participants in this study. Medical and research records will be maintained at each site in the strictest confidence. However, as a part of the quality assurance and legal responsibilities of an investigation, the investigational site will permit authorized representatives of regulatory authorities and NIAID to examine (and when required by applicable law, to copy) clinical records for the purpose of quality assurance reviews, audits, and evaluations of the study safety and progress. Unless required by the laws that permit copying of records, only the coded identity associated with documents or with other participant data may be copied (and all personally identifying information will be removed). Authorized representatives as noted above are bound to maintain the strict confidentiality of medical and research information that is linked to identify individuals.

